Data analysis:	
In this study, both patients and eyes will be considered as the analysis unit. Baseline characteristics will be summarized using descriptive statistics. For continuous variables, the mean, standard deviation, median and range will be presented. For categorical variables frequency and proportion will be used. Variables are identified and calculated at the index diagnosis and throughout the follow-up period for primary outcomes like VA.
 
In the progression analysis, the population will be restricted to patients with a minimum follow-up time (i.e. multiple visits at least one year apart, at least two years), or patients with valid VA reading at the index diagnosis and a second follow-up timepoint. [REDACTED]
 
The analysis of incident and prevalent calculations will use as the denominator, all patients referred to the retinal specialist. The proportion of patients with a GA diagnosis referred to the retinal specialist will be put into perspective by comparing to other conditions, such as proportion of patients referred to the retinal specialist with a diabetic macular edema (DME) diagnosis, or with a diabetic retinopathy (DR) diagnosis etc. Additionally, extrapolations will be done to approximate to a population-based estimate.
									
Milestones:	
 
 Start of data collection	05/2023		
 
 End of data collection	06/2023		
 
 Final report of study results	06/2023		
 
	Start of data collection	05/2023		End of data collection	06/2023		Final report of study results	06/2023	
Start of data collection	05/2023									
End of data collection	06/2023									
Final report of study results	06/2023									

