7. RATIONALE AND BACKGROUND

GA is the late-stage form of dry age-related macular degeneration (AMD) and responsible for 10-20% of the legally blind cases. Currently, there is only one treatment for GA available for patients, [REDACTED] is not approved by EMA yet and therefore not available for patients in Europe. Patients with wet AMD (wAMD), another advanced form of AMD, can be treated with Anti-VEGF treatment.

Presently, Boehringer Ingelheim (BI) is developing potential treatments for the target population of patients with GA secondary to AMD [REDACTED]

There are many unknowns regarding the natural history of patients with GA, and limited data on the prevalence, incidence, and progression of the disease. Recent results from clinical trials developing treatments for GA [REDACTED] found a substantial number of patients with wAMD in the fellow eye or converting to wAMD (20 to 40%) [REDACTED]

[REDACTED] the [REDACTED] a high rate of conversion to wAMD in the study eye occurred. This high rate of conversion may be influenced by the proportion of patients with wAMD present in the fellow eye. This project aims to provide clarity on the proportion of patients in the real world, with GA, wAMD in both study and fellow eyes, and the conversion rates, describing also functional and imaging results and treatment patterns.

BOEHRINGER INGELHEIM Group of Companies

NIS Protocol Template

Page 11 of 30

Study number: 1484.0014

Document number: <insert>

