9. RESEARCH METHODS

9.1 STUDY DESIGN

This is an observational cohort study based on existing data.

BOEHRINGER INGELHEIM Group of Companies**NIS Protocol Template****Study number: 1484.0014****Page 12 of 30****Document number: <insert>****9.1.1 Study population**

Study inclusion criteria: All patients ≥ 50 years, with a GA diagnosis in at least one eye, including in the [REDACTED] database identified during the study period (January 2015 to April 2023).

Exclusion criteria: Patients without the information of laterality will be excluded.

No other exclusion criteria are applied for the identification of the study population and description of the patients and eye at baseline.

Additional note:

For certain analysis the patient population will be restricted to those with at least 12, 24, 36, 48, or 60 months of history following diagnosis of GA. For the analysis requiring a VA reading, a restriction to those patients with valid VA readings at the index diagnosis and the respective follow-up times will be applied.

For analysis estimating the size of the GA population relative to other retinal diseases, the same timeframe requirements that the study population will be applied. In this population, any patient in the database will be eligible, and the diagnosis of DME, DR or other conditions may be used for subgroup comparisons.

Primary Disease Definitions

In the [REDACTED] Database, retinal and other diseases are identified using the International Classification of Diseases (ICD), Tenth Revision, Clinical Modification. ICD 10 codes were launched in the USA in October 2015, and are the only version of ICD codes with adequate descriptions of GA and dry AMD severity. As such, only ICD 10 codes will be analyzed in this study and the study period defined above is directly related to the launch of ICD 10 plus a small buffer allowing for physician familiarity.

These codes are entered by the physician at patient visit, with an associated laterality. This, along with the ICD 10 laterality is used in combination to confirm in which eye the disease is occurring. For this study, a patient eye will be considered to have the study disease so long as there is an accompanying ICD code. The primary study diseases to be analyzed are dry AMD, GA and wAMD, and will be identified using the ICD codes in Table 1 below.

Table 1. Study disease definitions-codes.

Study Disease Definitions			
	Dry AMD*	Dry AMD with GA*	wAMD*

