Prevalent visit – all visits following the incident visit in patient eye history while identified with GA in the [REDACTED] database. Prevalent visits may occur year after year throughout the patients' journey.

Study period

Patients will be identified from January, 2015 to April, 2023.

Selection period: Eligible patients must have at least one GA diagnosis between October 2015 and April 2023. The date of the first GA diagnosis will be considered as index date. For all follow up analysis, eligible patient eyes should be divided in those with at least 12, 24, 36, 48 and 60+ months of follow up. follow up requires multiple visits spanning over the outlined durations and total follow up is defined as the time between incident diagnosis and the final visit in the dataset.

BOEHRINGER INGELHEIM Group of Companies**NIS Protocol Template****Page 14 of 30****Study number: 1484.0014****Document number: <insert>**

Follow-up period: up to 60-month period following the index diagnosis date of GA (exploratory follow-up of 1, 2, 3, 4, 5 years may be run as cutoff points)

Pre-selection period: January 2015-September 2015. This period will be used to identify patients who have dry AMD using ICD9 coding, and will help to assign patients into the incidence or prevalence status.

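### The progression analysis is restricted by visits made after index, so observed conversions can be discarded and each year's rate comes from a differently selected set

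*Combined protocol and SAP*

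**What the plan says.** Three places set the population for follow-up analyses.

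- Section 9.1.1, Study period: for all follow-up analyses, "eligible patient eyes should be divided in those with at least 12, 24, 36, 48 and 60+ months of follow up". The text then explains that "follow up requires multiple visits spanning over the outlined durations" and that "total follow up is defined as the time between incident diagnosis and the final visit in the dataset". Follow-up is therefore attendance, not the calendar time available.
- Section 9.1.1, Additional note: for certain analyses, "the patient population will be restricted to those with at least 12, 24, 36, 48, or 60 months of history following diagnosis of GA".
- Section 4 (Abstract), Data analysis, on how progression will be analysed: "the population will be restricted to patients with a minimum follow-up time (i.e. multiple visits at least one year apart, at least two years". The sentence goes on to offer an alternative route, a valid VA reading at index and at a second timepoint, and redacted text follows.

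Other places bear on the same analysis. Section 9.2.1 lists duration of follow-up as a subgroup, to be examined after the overall population. Section 9.7.1 says GA patients are analysed as an overall group and that progression is assessed by time-to-event analysis. The same section makes Kaplan-Meier or Cox optional for progression, and states censoring at the final visit only for conversion from dry AMD to GA. Section 9.9 notes the short follow-up and proposes restricting to patients with at least two entries. It mentions Kaplan-Meier as a possible alternative.

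**The concern.** Entry to an N-month set depends on something that happens after index: still attending at N months. An eye that converts at month 8 and is last seen at month 11 enters none of the bands, although its conversion was recorded. The 12-, 24-, 36-, 48- and 60-month figures then come from five different sets, each more selected on attendance than the one before, and cannot be read as one course.

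This affects a primary objective. Section 8 asks for the progression of newly diagnosed GA in each of five years, and Section 7 gives real-world conversion rates as a reason for the study.

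Attendance could plausibly depend on the outcome. Section 7 says patients with wAMD "can be treated with Anti-VEGF treatment", and Section 9.3.2.2 lists treatment among the common reasons for a visit. Section 9.9 concedes a possible bias towards regular attenders for VA and other key clinical outcomes, but does not apply this to the follow-up restriction on conversion.

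**Working it through.** **What can be reproduced.** The plan gives no conversion rate, retention rate or sample-size formula to re-derive. Section 9.5 gives feasibility counts: 72,718 patients and 113,408 eyes with GA; 20,503 patients and 31,647 eyes with visits after 3 years; average follow-up 22 months. Section 9.9 gives a mean of 1.9 years. 22/12 = 1.83 years, which agrees with 1.9 only through rounding.

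**Step 1. Share with visits after 3 years.**
- Patients: 20,503/72,718 = 28.2%.
- Eyes: 31,647/113,408 = 27.9%.

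**Step 2. Separate calendar time from attendance.** Assume index dates are uniform over a window of L months. The share with 36 months of opportunity is (L − 36)/L. The feasibility cut date is not stated, so both ends of the window are varied.

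| Window | L | (L − 36)/L | 28.2% ÷ that share |
|---|---|---|---|
| Jan 2016 to Dec 2022 | 84 | 57.1% | 49.3% |
| Oct 2015 to Dec 2022 | 87 | 58.6% | 48.1% |
| Jan 2016 to Apr 2023 | 88 | 59.1% | 47.7% |
| Oct 2015 to Apr 2023 | 91 | 60.4% | 46.7% |

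About 47% to 49% of patients with the opportunity would meet a 36-month visit rule. About half would fail it because of attendance.

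**Step 3. Kaplan-Meier inside a restricted set.** If every eye must have at least N months of follow-up, no event-free eye is censored before N. The Kaplan-Meier estimate at N months is then the number converted divided by the number in the set, which is the crude restricted proportion. The method cannot restore the excluded eyes.

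**Step 4. Illustrative size.** All inputs here are assumptions, except that attendance is set from Step 2. Let conversion have constant hazard λ, and let loss have constant hazard d0 before conversion and d1 = r·d0 after it. With T = 36 months:
- attending and unconverted: u = exp(−(λ + d0)T)
- attending and converted: c = λ·exp(−d1·T)·[1 − exp(−aT)]/a, where a = λ + d0 − d1
- restricted proportion = c/(u + c), with d0 chosen so that u + c = 47.8%.

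For a true 36-month conversion of 20%, λ = −ln(0.80)/36 = 0.0062 per month. Then:
- r = 1.25: u = 0.3892, c = 0.0888, giving 18.6%
- r = 0.5: u = 0.3654, c = 0.1126, giving 23.6%
- r = 0.25: u = 0.3545, c = 0.1235, giving 25.8%.

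| True conversion | r = 1.25 | r = 1 | r = 0.75 | r = 0.5 | r = 0.25 |
|---|---|---|---|---|---|
| 10% | 9.2% | 10.0% | 10.9% | 11.9% | 13.1% |
| 20% | 18.6% | 20.0% | 21.6% | 23.6% | 25.8% |
| 40% | 37.8% | 40.0% | 42.6% | 45.7% | 49.6% |

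Moving attendance from 40% to 60% changes the entry for true 20% and r = 0.5 from 24.5% to 22.4%.

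**Step 5. The alternative.** Kaplan-Meier on all eyes from index, with unconverted eyes censored at last visit, was simulated under the same scenarios (200,000 eyes each). It returned about 10%, 20% and 40%, the true values, within simulation error. This holds when loss before conversion is unrelated to the risk of conversion.

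**The case against.** The strongest reply is that the bands are descriptive. Section 9.1.1 says eyes are divided, its note limits the restriction to certain analyses, Section 9.2.1 treats duration as a subgroup after the overall analysis, and Section 9.7.1 plans time-to-event analysis with GA patients as an overall group. Section 9.9 also says patients who leave are dropped from that point onwards, which sounds like censoring. On this reading an early converter is missing only from the duration subgroups.

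Part of this stands: it cannot be said that every planned conversion analysis loses such events. But the abstract applies the restriction to the progression analysis by name, and nothing in Sections 9.2.1, 9.7.1 or 9.9 overrides it. Kaplan-Meier is optional, and explicit censoring at the final visit is given for a different transition. The first remedy in Section 9.9 is a further restriction on entries.

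Three stronger readings are tempting, and the documents do not support them.
- A reader might infer that conversion rates will be too high because treatment keeps converters attending. No attendance by conversion status is given. Every visit counts for both eyes (Section 9.3.2.2), so disease in the fellow eye may keep a stable study eye under observation.
- A reader might infer that attendance removes 72% of patients from the 36-month set. That figure includes patients diagnosed too recently to have 36 months.
- A reader might infer that the abstract requires two years of everyone, in flat contradiction of the 12-month band. Its sentence continues with the VA route, redacted text follows, and the one-year and two-year phrases may be a list of thresholds. The wording needs reconciling; a contradiction is not proved.

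**Conclusion.** The point holds for the restriction as written. It conditions conversion rates on attendance after index, allows recorded conversions to be discarded, and makes the yearly figures non-comparable; time-to-event methods inside the restricted set do not repair this. The overall-group wording leaves room for a sound analysis but does not secure it.

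Direction and size remain unknown. The shift from 20% to between 18.6% and 25.8% is an illustration. It rests on uniform index dates, constant hazards and assumed loss ratios, and on feasibility counts that also used exam notes. The bias is zero if loss is the same before and after conversion, and downward if converters leave more readily. Description at index is unaffected, since Section 9.1.1 applies no follow-up restriction there.

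**What to change.** For conversion to wAMD (study and fellow eye) and to GA (fellow eye):

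1. Include every eye free of the event in question at index, with no minimum follow-up and no minimum number of visits.
2. Count events from index and censor event-free eyes at their last visit.
3. Make Kaplan-Meier (or cumulative incidence) at 12, 24, 36, 48 and 60 months the main estimate, not an option. No filter on calendar opportunity is needed, because censoring already handles recently diagnosed eyes and a filter would discard them.
4. Use the 12 to 60+ month bands only to describe follow-up, and reconcile the minimum follow-up wording in the abstract and in both parts of Section 9.1.1.
5. Keep the restriction to available readings for VA change only, where a follow-up reading is unavoidable.
6. Compare retained with lost eyes on index characteristics, and add a sensitivity analysis for informative loss, for example inverse-probability-of-censoring weights. Censoring at last visit can itself be informative, and Section 9.9 says death cannot be told apart from other loss.

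The cost is protocol wording, a changed cohort filter and a little more analysis, with no new data. Later-year estimates will rest on more heavily censored data.

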9.2 SETTING**9.2.1 Study sites**

All data in this study is de-identified, from existing electronical health records from the retinal specialist practices included in the [REDACTED] Database (US).

The [REDACTED] database consists of data from a geographically diverse panel of United States based private retina specialists (RS). [REDACTED] has physician coverage from 2015 onwards, totaling up to 360+ physicians coming from 70+ practices. These practices span across the USA geographically, with the regional distribution as follows: Midwest (20%), Northeast (17%), Southeast (27%), Southwest (11%), West (26%). This collection of practices has contributed 2+ million patients and 13+ million patient visits over the lifetime of [REDACTED] and is estimated to account for 15-20% of all retina specialists practicing in the USA. This dataset represents a collection of private practicing retina specialists in the USA, no data is collected from hospital or public institutions.

The [REDACTED] Database therefore includes longitudinal measures of physician findings and patient outcomes. This includes health related outcomes such as deterioration of visual acuity, poor adherence, subretinal fluid, intraocular pressure, and geographic atrophy. Patient phenotypes and individual outcomes can be described by individual comorbidities, demographics, visits, prescriptions, and other relevant clinical characteristics gathered from clinical codes, patient provided information and text mining of patient notes.

Study Subgroups

Following analysis on the overall population, subjects will be placed into subgroups for further analysis. Below are the proposed subgroups which may be subject to modification following data readouts. An initial feasibility will be run to assess each threshold for each subgroup, following which a final subgroup will be chosen. Any analysis (i.e. description of patients characteristics and progression) on subgroups will be defined below.

- Duration of follow up: 1+, 2+ 3+, 4+,5+ years of history
- Newly diagnosed patients with GA vs. patients with an existing GA diagnosis
- Conversion rates over time – Stratify the population into those that either progress/don't progress in the 1+, 2+ 3+, 4+,5+ years of follow up;
- [REDACTED] in the 1, 2, 3, 4 and 5 years of follow up period.
- Patients [REDACTED] that do not in the 1, 2, 3, 4 and 5 years of follow up period.

- GA lesion location (sub foveal vs extrafoveal)
- GA lesion size.

9.2.2 Study visits

As this is an observational study based on existing data, no study visit plan is applicable in this study.

9.2.3 Study discontinuation

This is an observational study based on existing data. No enrollment of patients is planned. Boehringer Ingelheim reserves the right to discontinue the study overall at any time for the following reasons:

1. Emergence of any effectiveness/safety information that could significantly affect continuation of the study, or any other administrative reasons
2. Violation of Good Pharmacoprevalence Practice (GPP), the study protocol, or the contract by a study site, investigator or research collaborator, disturbing the appropriate conduct of the study

The investigator/ the study site/research collaborator will be reimbursed for reasonable expenses incurred in case of study/site termination (except in case of the third reason).

9.3 VARIABLES

9.3.1 Exposures

Study Treatments

The treatment variables below are identified at the patient eye level and will be used to describe the treatment patterns throughout the analysis. These treatment variables will be analyzed throughout the entire study period. Each treatment type can only occur once per patient eye visit and will be identified at every distinct visit where the following codes are present. Treatment must contain both the Current Procedural Terminology (CPT) codes for intravitreal injection and the J-codes specifying the study treatment (Table 2).

Though not common, it is possible for multiple different treatment types to occur on the same day, in which case both treatments would be captured for analysis i.e., a patient could get a laser and an injection at the same visit.

Table 2. Study Treatment Definitions

Study Treatment Definitions		
Treatment	CPT Code	
		[REDACTED]
		[REDACTED], C9214, C9257, Q9977
		Eylea- J0178, C9291, Q2046
		Lucentis-J2778, C9233
		Beovu- J0179

BOEHRINGER INGELHEIM Group of Companies

NIS Protocol Template

Study number: 1484.0014

Page 16 of 30

Document number: <insert>

		Susvimo – C9093, J2779 Byooviz- Q5124 Vabysmo- J2777, C9097 Cimerli- C9097, Q5128
Corticosteroids	Intravitreal Injection – 67028	Ozurdex-J7312 Triamcinolone-J3300, J3301 Iluvien-J7313 Yutiq-J7314
Laser	Focal Grid Laser- 67210 Panretinal Photocoagulation- 67228	Not Applicable
C3 Inhibitor	[REDACTED]	J3490, C9399

[REDACTED] will also accept an incoming procedure medication that is associated to an [REDACTED]
[REDACTED]
[REDACTED]

9.3.2 **Outcomes**9.3.2.1 Primary outcomes

- [REDACTED]

This study will evaluate the disease progression over time. The main progression endpoints will be for the study eye, [REDACTED], changes in the GA lesion location, changes in the VA or changes in the size of the GA lesion. For the fellow eye the progression endpoints will also include the developing of GA.

*Please see Table 1, that includes the disease definitions (dry AMD, GA, and wAMD) based on ICD codes.

- **Position of GA lesion will be assessed over time.** The position of GA lesion will be defined using ICD 10 coding defined below. Any change in location status will be identified as progression of GA

Study Disease Definitions-lesion location		
	GA without Subfoveal Involvement	GA with Subfoveal Involvement
ICD 10	H35.3113, H35.3123, H35.3133, H35.3193,	H35.3114, H35.3124, H35.3134, H35.3194

BOEHRINGER INGELHEIM Group of Companies

NIS Protocol Template

Study number: 1484.0014

Page 17 of 30

Document number: <insert>

- **Increase in the size of GA lesion will be assessed over time.** The size of GA lesion will be further defined following feasibility of data availability, with the basis of the lesion size defined using text field extracts. An example of text entries available for classification are defined below. Note that any analysis involving lesion size will need to be run on a subset population where these data are available/documentated;
Small: “Non-Central Geographic Atrophy, Small.”;
Medium: “Moderate Geographic Atrophy (Juxtafoveal)”;
Large: “1.5 DD Central Geographic Atrophy, Large.”, “Central Geographic Atrophy, Large.”, “4+ Geographic Atrophy.”
- **Progression of GA by Visual Acuity**

Change in visual acuity over time will be tracked from the incident date of GA, and assessed on a yearly basis in order to track the progression of GA over time. In this study, visual acuity will be defined as follows:

[REDACTED] receives VA data from Snellen charts in over 98% of cases, with some other types (ex. Jaeger, charts) in the remainder. There are no instances of ETDRS being received since all data are coming from private retina clinics. All VA entries are standardized and converted to LogMAR for reporting purposes. [REDACTED] standard output for VA is in the form of [REDACTED]

[REDACTED] will only compare VA results of a patient if vision is taken by the same measurement method; i.e., if a patient has their vision recorded using a DCC measurement at index diagnosis, for the remainder of the study, only DCC measurements will be accepted for comparison. This is done to ensure that any change in VA is due to actual change in the patients' vision, and not due to them taking a different vision test. Further, where DCC is not available for VA, any other measurements will be used, ensuring the same type of measurement will be used for the same eye to estimate the changes over time. The ranking order for measurement types is DCC ->NCC ->PH ->DSc ->NSc.

When capturing VA at different time points of interest, a buffer is allowed on either side of the date to increase the chances of each eye coming in for a visit. Should an eye have 2 readings inside the buffer window, the reading closest to the date of interest is taken. The buffers are proposed as follows:

- Index Diagnosis: +/- 30 days
- Follow up reading at Month 6, 12, or 18: +/- 30 days
- Follow up reading at Month 24, 36, 60: +/- 60 days

Incidence (new cases) and prevalence of GA will be captured, based on the ICD 10 diagnosis codes. On a calendar basis, all newly diagnosed patients will be identified and count as incident patients. Patients with a previous diagnosis of GA in the past years (with respect to a given calendar year), will be counted as prevalent cases during that calendar year.

The yearly counts of newly diagnosed or prevalent cases, will help to understand the progression of the overall disease.

BOEHRINGER INGELHEIM Group of Companies**NIS Protocol Template****Study number: 1484.0014****Page 18 of 30****Document number: <insert>****9.3.2.2 Secondary outcomes****• Retinal Disease Related HCRU Outcomes**

Change in physician care over time will be evaluated from the incident date of GA, and assessed on a yearly basis in order to assess if physician habits have changed over time, particularly following September 2021 and additionally following [REDACTED].

Patient visits: A patient visit (or encounter) is identified in the database any time a patient visits one of the panel physicians. Since the [REDACTED] database consists only of private practicing retina specialists, these are the only types of visits analyzed in the study.

If a patient visits the physician at a hospital, institution, or has an emergency room admission, the event will not be captured. For all patient visits, it is assumed that both eyes are being seen/assessed even in the primary visit reason is for one particular eye. In this sense, all visits will contribute to both eyes and any outcomes at these visits will be available for assessment.

Treatments: The documentation includes **all treatments** including injections, laser treatments, and other procedures. The type of diagnostic procedure done, and the results of these diagnostics are also recorded for most encounters. For any visit, it is assumed that both eyes are being seen, even if only one eye receives any treatment.

Other medical procedures: for example, cataracts removal, eye lid (ptosis correction), etc.

Checkups: While these eyes may be on a different treatment regimen and are only observed at this visit, the physician will still track **VA**, **CRT** and perform **other** general check-ups. Common reasons for visits include treatment, check-up, post operative follow up, sudden vision issues, etc. Visit burden to the retina specialist will be analyzed for the duration of the study period and tracked year over year.

Ocular comorbidities (see section 9.3.3.2) will be described over the study period, yearly.

